7.10 Analysis of Key Secondary Endpoints

Health-related quality of life (HRQoL)

The increase in CWIS-PSDL scale scores from baseline to three and twelve weeks (separately) will be analysed in the same way as described in the primary endpoint analysis.

Increase from baseline scores to three, six, and twelve weeks will be calculated and analysed separately in the same way as described in the primary endpoint analysis for the following variables also:

- CWIS-SL scale
- CWIS-WB scale
- CWIS-GQ scale
- CWIS-SQ scale

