## 10.2 EFFICACY

### 10.2.1 Primary Efficacy

The primary objective of the study is to compare HRQoL in subjects with chronic wounds. The primary efficacy variable used to measure this objective will be the change from baseline in the CWIS-PSDL scale, over a six week treatment period.

The CWIS-PSDL scale is a 24 item questionnaire split into uses a 5 category Likert scale to answer each item with a 1 - 5 score assigned to each category. The first 12 items focus on whether the subject has experienced any of the items over the past 7 days [Not at all/Not applicable – 5, Seldom – 4, Sometimes – 3, Frequently – 2, Always – 1]. The last 12 items focus on how stressful the experience of the items has been over the past 7 days [Not at all/Not applicable – 5, Slightly – 4, Moderately – 3, Quite a bit – 2, Very applicable – 1]. These scores are then transformed into a 0-100 scale at each time point, where a high score represents a 'good' HRQoL and a low score represents a 'poor' HRQoL, using the following formula:

$$PSDL\ Score = \frac{Sum\ of\ item\ scores - 24}{96} \times 100$$

The increase in CWIS-PSDL score between baseline and 6 weeks will be derived as follows:

$$\text{PSDL score increase} = (\text{Score at 6 weeks} - \text{Score at baseline})$$

Subject responses to individual items at each assessment will be summarized as ordinal variables by treatment, wound type (and overall) and level of exudate at baseline.

The CWIS-PSDL score at Baseline and 6 weeks will be summarized as a continuous variable by treatment, wound type (and overall) and level of exudate at baseline.

The increase in CWIS-PSDL score between the Baseline and 6 weeks will be summarized as a continuous variable by treatment, wound type (and overall), baseline mobility, and level of exudate at baseline.

For the primary analysis, an ANCOVA model will be fit to the FAS population with the increase in CWIS-PSDL score between the Baseline and 6 weeks as the dependent variable, treatment (ALNB or SC) and center will be included in the model as fixed effects and subject will be included as a random effect. The covariates for the model to be considered will be wound type, baseline CWIS-PSDL score, baseline exudate level, baseline mobility, and baseline wound area.

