#### 10.2.2.1 *Key Secondary*

##### Health-related quality of life (HRQoL)

Subject-reported HRQoL variables (measured using the CWIS) include:

- The increase in CWIS-PSDL scale scores from baseline to three and twelve weeks (separately). This will be analyzed in the same way as described in the primary efficacy analysis.
- Increase from baseline scores to three, six, and twelve weeks will be calculated and analyzed separately in the same way as described in the primary efficacy analysis, for the following variables:
  - CWIS-SL scale
  - CWIS-WB scale
  - CWIS-GQ scale
  - CWIS-SQ scale

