7.4 Derived Data

Analysis Populations

- Indicator for inclusion in the safety population.
- Indicator for inclusion in the full analysis set population.
- Indicator for inclusion in the per protocol population.

Demographics, Baseline Data and Disposition Data

- Age = (Date of baseline visit – date of birth) /365.25

Note: Round down to the nearest whole number.

CONFIDENTIAL AND PROPRIETARY

This document contains information that is confidential and proprietary to Smith & Nephew PLC and Smith & Nephew, Inc. and is intended for use only by Smith & Nephew and its manufacturer. It shall not be reproduced or copied in whole or in part, nor shall the contents be disclosed by any means without prior written permission from Smith & Nephew, nor shall anyone make any use of it that is contrary to the expressed or implied wishes of Smith & Nephew

Statistical Analysis Plan	
A Pilot Randomized Controlled Trial to Evaluate an Advanced Borderless Dressing (ALLEVYN™ LIFE Non-Bordered) in the Treatment of Chronic Ulcers	Number: CT1603ALF ST: 1005 Version: 1.0, 27-Jul-2018 Page: 16 of 27

- Body Mass Index (BMI)[kg/m²] = weight [lbs] * 703.07/ (height [inches])²

Note: the 703.07 is to correct for using pounds and inches.

- Ulcer duration = Date of baseline visit – Date of ulcer onset
- Treatment duration [days] = Date of treatment discontinuation – date of baseline assessment.
- Duration between visits = Date of Study Visit_i – date of baseline assessment, where i = 2,3,4
- A flag for if the study visit occurs outside of the time range defined in the protocol i.e. Study Visit 2 should occur on Day 21 ± 3 days, Study Visit 3 should occur on Day 42 ± 4 days, End of Study Visit should occur on Day 84 ± 4 days.

Cardiff Wound Impact Schedule

- CWIS PSDL Score =
$$\frac{\text{Sum of PSDL item scores} - 24}{96} * 100$$
- CWIS SL Score =
$$\frac{\text{Sum of SL item scores} - 14}{56} * 100$$
- CWIS WB Score =
$$\frac{\text{Sum of WB item scores} - 7}{28} * 100$$
- The CWIS-GQ score is the number circled for “How good is your quality of life”
- The CWIS-PQ score is the number circled for “How satisfied are you with your overall quality of life”
- The below formula for individual domain increases from baseline applies to all the above mentioned CWIS domains:

CWIS domain Score increase = Score at visit_i – Score at baseline visit, i = 2,3,4

CONFIDENTIAL AND PROPRIETARY

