The increase in CWIS-PSDL score between the Baseline and 6 weeks will be summarized as a continuous variable by treatment, wound type (and overall), baseline mobility and level of exudate at baseline.

Primary Analysis of Primary Endpoint

For the primary analysis an ANCOVA model will be fit to the FAS population with the increase in CWIS-PSDL score between Baseline and 6 weeks as the dependent variable. The model will contain a term for treatment (ALNB or SC) and the following terms will be added to the model using a stepwise selection procedure with an F-value to attain a significance level of 0.1: centre, wound type and BMI, baseline CWIS-PSDL score.

The null hypothesis will be that there is no difference between the treatments in terms of the increase from baseline to 6 weeks in CWIS-PSDL score. An estimate of the LS mean

CONFIDENTIAL AND PROPRIETARY

This document contains information that is confidential and proprietary to Smith & Nephew PLC and Smith & Nephew, Inc. and is intended for use only by Smith & Nephew and its manufacturer. It shall not be reproduced or copied in whole or in part, nor shall the contents be disclosed by any means without prior written permission from Smith & Nephew, nor shall anyone make any use of it that is contrary to the expressed or implied wishes of Smith & Nephew

Statistical Analysis Plan	 Number: CT1603ALF ST: 1005 Version: 1.0, 27-Jul-2018 Page: 21 of 27
A Pilot Randomized Controlled Trial to Evaluate an Advanced Borderless Dressing (ALLEVYN™ LIFE Non-Bordered) in the Treatment of Chronic Ulcers	

difference between the treatments (ALNB – SC) for the CWIS-PSDL score will be reported, along with the corresponding 95% confidence interval and p-value.

If the assumptions of ANCOVA are not met then a non-parametric analysis will be considered the primary analysis for this variable. The same analysis will be done as for the parametric analysis however a Rank ANCOVA model will be used instead.

Secondary Analysis of Primary Endpoint

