7.11 Analysis of Secondary Endpoints

Modified Bates- Jensen Wound Assessment Tool

Part of the assessment of ulcer progression will be done using a modified version of the Bates- Jensen Wound Assessment tool assessing: undermining, necrotic tissue type, necrotic tissue amount, exudate type, exudate amount, skin color surrounding the wound, granulation tissue and epithelialization. Each item will be scored according to section 9.5.1 of the study protocol. A total score for each subject at each assessment will be calculated by summing the scores for all 8 items.

The total score for the modified Bates- Jensen Wound Assessment tool will be summarized using descriptive statistics at all visits by treatment and overall. Repeated measures ANCOVA model will be used with the total score as the dependent variable. As a minimum the model will contain terms for treatment, visit and a treatment-by-visit interaction term. The following terms will be added to the model using a stepwise selection procedure with an F-value to attain a significance level of 0.1: centre, wound

CONFIDENTIAL AND PROPRIETARY

This document contains information that is confidential and proprietary to Smith & Nephew PLC and Smith & Nephew, Inc. and is intended for use only by Smith & Nephew and its manufacturer. It shall not be reproduced or copied in whole or in part, nor shall the contents be disclosed by any means without prior written permission from Smith & Nephew, nor shall anyone make any use of it that is contrary to the expressed or implied wishes of Smith & Nephew

Statistical Analysis Plan	
A Pilot Randomized Controlled Trial to Evaluate an Advanced Borderless Dressing (ALLEVYN™ LIFE Non-Bordered) in the Treatment of Chronic Ulcers	Number: CT1603ALF
	ST: 1005
	Version: 1.0, 27-Jul-2018
	Page: 23 of 27

type, BMI and baseline CWIS-PSDL score. The difference in least squares mean (LSMean) between treatments at the 3, 6 and 12 week visit will be presented with the associated 95% confidence interval.

Other assessments of ulcer progression

- Condition of peri-wound (categorized as Normal, Erythematous, Edematous, Eczematous, Excoriated, Macerated, Indurated) at each post-baseline time point cross-tabulated with condition of peri-wound at baseline.

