- Ulcer length/width/depth will be used to derive area and volume. These variables will then be used to derive the reduction in area, depth, and volume from baseline to three, six and twelve weeks. The reduction in each dimension at each assessment (3, 6 and 12 weeks) will be analysed as the dependent variable in separate ANCOVA models. As a minimum the models will contain a term for treatment. The following terms will be added to the model using a stepwise selection procedure with an F-value to attain a significance level of 0.1: centre, subject, wound type, BMI and the relevant baseline wound dimension (area/ depth/ volume). The estimate difference in the LSMean reductions from baseline in area, depth, and volume (separately) between treatments will be presented with the associated 95% confidence interval.
- Reference ulcer healed (100% re-epithelialized, no drainage, no need for a dressing) will be summarized at each assessment (at three, six, and twelve weeks) and analyzed using a repeated measures logistic regression model with whether the reference ulcer was healed or not at the assessment as the dependent variable. As a minimum the model will contain a term for treatment. The following terms will be added to the model using a stepwise selection procedure with an F-value to attain a significance level of 0.1: centre, wound type and BMI..

Healthcare resource use

CONFIDENTIAL AND PROPRIETARY

This document contains information that is confidential and proprietary to Smith & Nephew PLC and Smith & Nephew, Inc. and is intended for use only by Smith & Nephew and its manufacturer. It shall not be reproduced or copied in whole or in part, nor shall the contents be disclosed by any means without prior written permission from Smith & Nephew, nor shall anyone make any use of it that is contrary to the expressed or implied wishes of Smith & Nephew

Statistical Analysis Plan	
A Pilot Randomized Controlled Trial to Evaluate an Advanced Borderless Dressing (ALLEVYN™ LIFE Non-Bordered) in the Treatment of Chronic Ulcers	Number: CT1603ALF
	ST: 1005
	Version: 1.0, 27-Jul-2018
	Page: 24 of 27

The following Healthcare resource variables will be summarized by treatment groups and overall (i.e. all assessments together) using continuous or categorical data summaries (as appropriate):

- Number and type of dressings used (both primary and secondary dressings), including use of compression therapy
- Number of outpatient visits

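### SAP 7.10 does not say that the SL, WB, GQ and SQ analyses use each scale's own baseline; read literally, the only baseline score available to those models is CWIS-PSDL

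*SAP*

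**What the plan says.** SAP 7.9 fits an ANCOVA to the six-week increase in CWIS-PSDL. Only treatment is always in the model. The other terms ("centre, wound type and BMI, baseline CWIS-PSDL score") enter "using a stepwise selection procedure with an F-value to attain a significance level of 0.1". The repeated-measures model in the same section offers the same candidates.

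SAP 7.10 then sends the increases in SL, WB, GQ and SQ at three, six and twelve weeks to be "analysed separately in the same way as described in the primary endpoint analysis". It names no covariates of its own. SAP 7.4 defines each outcome as a change from that scale's own baseline: "CWIS domain Score increase = Score at visit_i – Score at baseline visit, i = 2,3,4".

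The protocol has the same structure. Section 10.2.1 lists as possible covariates "wound type, baseline CWIS-PSDL score, baseline exudate level, baseline mobility, and baseline wound area", and section 10.2.2.1 has the other scales "analyzed separately in the same way as described in the primary efficacy analysis, for the following variables". SAP 7.15, which lists changes from the protocol, does not address the point.

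SAP 7.11 shows both practices. The ulcer-dimension models offer "the relevant baseline wound dimension (area/ depth/ volume" as a candidate. The model for the modified Bates-Jensen total, which is not a PSDL outcome, ends its candidate list with "type, BMI and baseline CWIS-PSDL score" and does not name the baseline Bates-Jensen total.

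**The concern.** A change score is negatively related to its own baseline, because subjects who start low tend to rise and those who start high tend to fall. Putting the own baseline in the model removes that variation from the residual. It also removes the effect on the treatment difference of any chance gap between the arms at baseline. Baseline PSDL does this only to the extent that it correlates with the scale being analysed.

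One programmer could follow 7.10 to the letter and use baseline PSDL, and another could substitute the matching baseline. Both could claim to follow the SAP, and their estimates would differ. Protocol 8.2 gives an effect-size estimate for a future trial as one purpose of this study. With about 40 subjects, precision and protection from chance imbalance are most of what the analysis can add.

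**Working it through.** **Sample size.** The plan's figure reproduces: 25 ALNB subjects at 5:3 give 25 × 8/5 = 40 in total and 25 × 3/5 = 15 on SC. The plan states no SD, correlation or power (SAP 6.1).

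**Assumptions, not in the documents.** All variances are 1. The correlation of a scale's baseline with its own follow-up is ρ = 0.3 to 0.7. The correlation of that baseline with baseline PSDL is r = 0.5 to 0.7. PSDL relates to follow-up only through the own baseline, so its correlation with follow-up is ρr. Covariates are forced in.

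**Formulas.**
- Chance baseline difference, SD: k = √(1/25 + 1/15) = 0.327 of a scale SD
- Residual variance of change, no baseline score: 2(1−ρ)
- Residual variance given baseline PSDL: 2(1−ρ) − r²(1−ρ)²
- Residual variance given own baseline: 1−ρ²
- Standard error (SE) = k × √(residual variance)
- Share of own-baseline imbalance left with PSDL in the model: (1−ρ)(1−r²), with sign opposite to the imbalance

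**Worked ends of the range.**
- ρ = 0.3, r = 0.5: variance given PSDL 1.4 − 0.1225 = 1.2775, given own baseline 0.91. √(1.2775/0.91) = 1.185. Share left 0.7 × 0.75 = 0.525.
- ρ = 0.7, r = 0.7: variance given PSDL 0.6 − 0.0441 = 0.5559, given own baseline 0.51. √(0.5559/0.51) = 1.044. Share left 0.3 × 0.51 = 0.153.

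| ρ | r | SE, own | SE, PSDL | Excess, PSDL | Excess, no baseline | Shift for a one-SD (0.327) imbalance |
|---|---|---|---|---|---|---|
| 0.3 | 0.5 | 0.312 | 0.369 | 18.5% | 24.0% | 0.17 SD |
| 0.3 | 0.7 | 0.312 | 0.352 | 12.9% | 24.0% | 0.12 SD |
| 0.5 | 0.5 | 0.283 | 0.316 | 11.8% | 15.5% | 0.12 SD |
| 0.5 | 0.7 | 0.283 | 0.306 | 8.2% | 15.5% | 0.08 SD |
| 0.7 | 0.5 | 0.233 | 0.248 | 6.4% | 8.5% | 0.07 SD |
| 0.7 | 0.7 | 0.233 | 0.244 | 4.4% | 8.5% | 0.05 SD |

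At 25 v 15, an own-baseline gap above 0.3 SD has probability 36%, and one above 0.5 SD has probability 13%.

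**Effect of stepwise entry.** The table forces the covariate in, and the SAP does not. A simulation of 6,000 trials per row, with one baseline score as the only candidate and entry at p < 0.1, kept baseline PSDL in 32% to 85% of trials. The own baseline, offered as a candidate instead, was kept in 80% to 99%. The spread of the estimate under the PSDL-candidate rule, against own baseline forced in, ran from 0.377/0.315 = 1.20 (first row) to 0.243/0.230 = 1.06 (last row). With own baseline as a mere candidate the spread was close to the forced value, at worst 0.239 against 0.235.

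**Repeated-measures version.** There the outcome is the score itself. If 7.10 extends to that model and only post-baseline visits are fitted, the per-visit SE ratio is √[(1−ρ²r²)/(1−ρ²)]. This runs from √(0.9559/0.91) = 1.02 (ρ = 0.3, r = 0.7) to √(0.8775/0.51) = 1.31 (ρ = 0.7, r = 0.5). The share of imbalance left is ρ(1−r²), again 0.153 to 0.525.

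**The case against.** The best reply is that the literal reading is selective. SAP 7.9 names CWIS-PSDL in the dependent variable, the baseline candidate, the null hypothesis and the reported difference. Applying the method to another scale already requires replacing PSDL in three of these places, and doing so in the fourth gives the matching baseline. The closest analogue, the change-from-baseline ANCOVA for ulcer dimensions, names the own baseline. The Bates-Jensen model writes out its own list, so it is not a cross-reference. This stands to the extent that 7.10 is ambiguous. It does not make substitution safe to assume, because the Bates-Jensen model shows the SAP naming baseline PSDL for an outcome that is not PSDL.

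A reader might infer three stronger claims that the documents do not support:

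- *That the 12 analyses will be adjusted for PSDL and never for their own baseline.* PSDL is only a candidate and may drop out. The text does not exclude substitution, and the own baseline already enters through the change score.
- *That the estimates are biased.* The change score subtracts the imbalance. What remains is regression to the mean, which averages zero under randomisation and is already reflected in the wider standard error.
- *That several points are at stake on every scale.* With an assumed SD of 20, a one-SD imbalance of 6.5 points would leave 1.0 to 3.4 points. That can apply only to SL and WB, scored 0 to 100. GQ and SQ are single items scored 0 to 10 (Protocol 21.2, SAP 7.4). Even for SL and WB, the 95% half-width on these assumptions is about 10 to 15 points (1.96 × 20 × 0.244 to 0.369).

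It is also fair that these are secondary endpoints of a pilot without multiplicity control (SAP 7.8), and that Protocol 5.6 does not expect significant differences. That limits the consequence. It does not affect the case for a better estimate at no cost.

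**Conclusion.** The point holds as a gap in specification. SAP 7.10 does not say which baseline score is the candidate for SL, WB, GQ and SQ, and on a literal reading it is PSDL or none. The cost of that reading is an SE about 4% to 19% larger than with the own baseline, with 15% to 53% of a chance own-baseline imbalance left in the estimate. If PSDL drops out, the excess is 8.5% to 24% (ρ 0.7 to 0.3).

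These figures rest on the assumed correlations, on forced covariates, and on PSDL acting only through the own baseline. The upper ends need a within-scale correlation as low as 0.3; at ρ = r = 0.7 the cost is about 4%. The change is a free improvement with a modest gain.

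**What to change.** In SAP 7.10 write: *as in the primary endpoint analysis, with the baseline score of the scale being analysed in place of baseline CWIS-PSDL*. Apply this to SL, WB, GQ and SQ at every visit and in any repeated-measures version. Preferably make that baseline a fixed term, since a bare swap leaves it a stepwise candidate that may drop out. Check the Bates-Jensen model in SAP 7.11 in the same way.

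The cost is one sentence, plus a matching edit in 7.11 if wanted. The CWIS is already completed at Visit 1, so no new data, visits or subjects are needed.

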7.11 Analysis of Secondary Endpoints

Modified Bates- Jensen Wound Assessment Tool

Part of the assessment of ulcer progression will be done using a modified version of the Bates- Jensen Wound Assessment tool assessing: undermining, necrotic tissue type, necrotic tissue amount, exudate type, exudate amount, skin color surrounding the wound, granulation tissue and epithelialization. Each item will be scored according to section 9.5.1 of the study protocol. A total score for each subject at each assessment will be calculated by summing the scores for all 8 items.

The total score for the modified Bates- Jensen Wound Assessment tool will be summarized using descriptive statistics at all visits by treatment and overall. Repeated measures ANCOVA model will be used with the total score as the dependent variable. As a minimum the model will contain terms for treatment, visit and a treatment-by-visit interaction term. The following terms will be added to the model using a stepwise selection procedure with an F-value to attain a significance level of 0.1: centre, wound

CONFIDENTIAL AND PROPRIETARY

This document contains information that is confidential and proprietary to Smith & Nephew PLC and Smith & Nephew, Inc. and is intended for use only by Smith & Nephew and its manufacturer. It shall not be reproduced or copied in whole or in part, nor shall the contents be disclosed by any means without prior written permission from Smith & Nephew, nor shall anyone make any use of it that is contrary to the expressed or implied wishes of Smith & Nephew

Statistical Analysis Plan	
A Pilot Randomized Controlled Trial to Evaluate an Advanced Borderless Dressing (ALLEVYN™ LIFE Non-Bordered) in the Treatment of Chronic Ulcers	Number: CT1603ALF
	ST: 1005
	Version: 1.0, 27-Jul-2018
	Page: 23 of 27

type, BMI and baseline CWIS-PSDL score. The difference in least squares mean (LSMean) between treatments at the 3, 6 and 12 week visit will be presented with the associated 95% confidence interval.

Other assessments of ulcer progression

- Condition of peri-wound (categorized as Normal, Erythematous, Edematous, Eczematous, Excoriated, Macerated, Indurated) at each post-baseline time point cross-tabulated with condition of peri-wound at baseline.
- Ulcer length/width/depth will be used to derive area and volume. These variables will then be used to derive the reduction in area, depth, and volume from baseline to three, six and twelve weeks. The reduction in each dimension at each assessment (3, 6 and 12 weeks) will be analysed as the dependent variable in separate ANCOVA models. As a minimum the models will contain a term for treatment. The following terms will be added to the model using a stepwise selection procedure with an F-value to attain a significance level of 0.1: centre, subject, wound type, BMI and the relevant baseline wound dimension (area/ depth/ volume). The estimate difference in the LSMean reductions from baseline in area, depth, and volume (separately) between treatments will be presented with the associated 95% confidence interval.
- Reference ulcer healed (100% re-epithelialized, no drainage, no need for a dressing) will be summarized at each assessment (at three, six, and twelve weeks) and analyzed using a repeated measures logistic regression model with whether the reference ulcer was healed or not at the assessment as the dependent variable. As a minimum the model will contain a term for treatment. The following terms will be added to the model using a stepwise selection procedure with an F-value to attain a significance level of 0.1: centre, wound type and BMI..

Healthcare resource use

CONFIDENTIAL AND PROPRIETARY

This document contains information that is confidential and proprietary to Smith & Nephew PLC and Smith & Nephew, Inc. and is intended for use only by Smith & Nephew and its manufacturer. It shall not be reproduced or copied in whole or in part, nor shall the contents be disclosed by any means without prior written permission from Smith & Nephew, nor shall anyone make any use of it that is contrary to the expressed or implied wishes of Smith & Nephew

Statistical Analysis Plan	
A Pilot Randomized Controlled Trial to Evaluate an Advanced Borderless Dressing (ALLEVYN™ LIFE Non-Bordered) in the Treatment of Chronic Ulcers	Number: CT1603ALF
	ST: 1005
	Version: 1.0, 27-Jul-2018
	Page: 24 of 27

The following Healthcare resource variables will be summarized by treatment groups and overall (i.e. all assessments together) using continuous or categorical data summaries (as appropriate):

- Number and type of dressings used (both primary and secondary dressings), including use of compression therapy
- Number of outpatient visits
- Amount of time in hospital (nights spent as an inpatient)
- Number and type of interventions/procedures including debridement of ulcer (curette, scissors, scalpel, forceps, other)
- Number and type of concomitant therapies/treatments

